##### Adverse Events of Special Interest (AESI)

Infusion-related reactions presenting as hypersensitivity/allergic reaction, anaphylaxis, or cytokine release syndrome as well as inhalation-related reactions presenting as allergic reaction (e.g., bronchospasm that may manifest with wheezing and/or respiratory distress) are designated as Adverse Events of Special Interest (AESIs).

Infusion of biological products including monoclonal antibodies may be associated with the development of infusion-related reactions that can occur during and/or within hours of the infusion. Symptoms of infusion-related reactions may be related to immediate hypersensitivity (allergic reaction, anaphylaxis) or cytokine release syndrome. Symptoms of cytokine release syndrome may include, but are not limited to, fever, tachypnea, headache, tachycardia, hypotension, all types of rashes including flushing, and/or hypoxia.

Inhalation of pharmaceutical agents may result in airway irritation and/or hypersensitivity that can result in bronchospasm manifesting with wheezing, prolonged expiration and respiratory distress.

The presence or absence of infusion-related reactions presenting as hypersensitivity/allergic reaction, anaphylaxis, or cytokine release syndrome, as well the presence or absence of inhaled-related reactions presenting as allergic reaction (e.g., bronchospasm) will be solicited and documented until the study visit seven days after study drug administration.

Adverse Events of Special Interest should be communicated to the Sponsor in an expedited manner (see section 9.3.1 for requirements).

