#### Allergic/Anaphylactic reactions

Administration of non-human, chimeric, or humanized antibodies can result in severe allergic and anaphylactic reactions because the non-human derived components can be recognized as foreign by the recipient's immune system. In contrast, administration of human immunoglobulins (e.g., IVIG, hepatitis B immunoglobulin) is a routinely performed and safe clinical procedure for the treatment of autoimmune diseases or immune deficiency or to prevent viral infections such as hepatitis B. Similarly, monoclonal antibodies of human origin have been shown to be generally safe and well tolerated. DZIF-10c is derived from a human antibody that naturally developed in response to SARS-CoV-2 infection and was recombinantly produced in a mammalian cell line without use of animal-derived media components. DZIF-10c has not been administered to humans prior to this study and thus, no clinical data on the tolerability of DZIF-10c is available.

*Risk mitigation strategy:* DZIF-10c by inhalation will be administered slowly over a period of approximately 15-20 minutes under supervision. DZIF-10c by infusion will be administered slowly over an approximately 60-minute infusion. During the dose escalation phase, participants will be hospitalized for the inhalation for immediate access to emergency therapy. Antiinflammatory medication, bronchodilators, emergency kits and an intensive-care unit are available on-site. Infusion- and inhalation-related reactions will be solicited as Adverse Events of Special Interest (AESIs) until the trial visit scheduled for day 7 after study drug administration.

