### Irritation of Airways

Administration of DZIF-10c and excipients may result in airway irritation that could manifest as cough, wheezing, bronchial narrowing, or bronchospams resulting in respiratory distress.

*Risk mitigation strategy:* Inhalators and/or nebulizers for the application of bronchodilators will be available at the site of the trial drug administration. Inhalation-related reactions will additionally be solicited as Adverse Events of Special Interest (AESIs) until the trial visit scheduled for day 7 after study drug administration.

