#### Adverse Events of Special Interest

Infusion-related reactions presenting as hypersensitivity/allergic reaction, anaphylaxis, or cytokine release syndrome; as well as inhalation-related reactions presenting as allergic reaction (e.g., bronchospasm that may manifest with wheezing and/or respiratory distress) are designated as Adverse Events of Special Interest. For details of reporting requirements, see section 9.3.1.

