7.8.1 Adverse Events

Unless otherwise specified, the analyses of adverse events (AEs) will be descriptive in nature. All analyses of AEs will be based on the number of subjects with AEs and NOT on the number of AEs.

For analysis multiple AE occurrence data on the eCRF will be collapsed into an AE provided that all of the following applies:

- All AE attributes are identical (LLT, intensity, action taken, therapy required, seriousness, reason for seriousness, relationship, outcome, AESI and CTCAE grade (based on version 5)).
- The occurrences were time-overlapping or time-adjacent (time-adjacency of 2 occurrences is given if the second occurrence started on the same day or on the day after the end of the first occurrence).

The analysis of AEs will be based on the concept of treatment emergent AEs. That means that all adverse events occurring after drug intake until the end of the residual effect period (+90 days thereafter) (+7 and +28 days as additional analysis) will be assigned to the treatment. In addition, AEs starting from day 9 until day 91 will be tabulated separately. All adverse events occurring before drug intake will be assigned either to 'screening' or 'post-randomisation' (phase IIa part and for listings only). All adverse events occurring after drug intake +90 days will be assigned to 'post-study' (for listings only). For details on the treatment definition, see [Section 6.1](#).

Adverse events related to infusion-related reactions (AEs presenting as hypersensitivity/allergic reaction, anaphylaxis, or cytokine release syndrome) as well as inhalation-related reactions presenting as allergic reaction (e.g., bronchospasm that may manifest with wheezing and/or respiratory distress) will be considered as protocol-specified AESIs, and ticked as such in the eCRF. Further adverse event groupings by safety topic have been defined outside the trial protocol, which will be continuously updated at project level (2). These safety topics are deemed of particular importance, and these definitions can be based on selection of coded terms

based on MedDRA. The latest approved version of the project level overview archived prior to either DBL will be used in the corresponding CTR.

An overall summary of adverse events having occurred during trial participation will be presented, including all AEs occurring:

- Within the first 7 days after drug administration
- Within the first 28 days after drug administration (sensitivity analysis)

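### Protocol 4.2.1 relies on AESI solicitation to cover airway irritation, but the operative definitions admit only allergic presentations, so non-serious, non-DLT irritation can be missed or counted unevenly

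*Protocol*

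**What the plan says.** Protocol 4.2.1 treats allergic or anaphylactic reactions and irritation of the airways as two separate risks. On irritation it says that DZIF-10c and its excipients "may result in airway irritation that could manifest as cough, wheezing, bronchial narrowing, or bronchospams resulting in respiratory distress". Apart from having bronchodilators at hand, the mitigation it offers is this: "Inhalation-related reactions will additionally be solicited as Adverse Events of Special Interest (AESIs) until the trial visit scheduled for day 7". No allergic mechanism is required.

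The operative definitions add one. Protocol 5.2.1 states that "inhalation-related reactions presenting as allergic reaction (e.g., bronchospasm that may manifest with wheezing and/or respiratory distress) are designated as" AESIs, and a later paragraph of the same section limits what is solicited to day 7 in the same way. Protocol 9.1.1 repeats the condition ("as well as inhalation-related reactions presenting as allergic reaction"). SAP 7.8.1 follows: "inhalation-related reactions presenting as allergic reaction (e.g., bronchospasm that may manifest with wheezing and/or respiratory distress) will be considered as protocol-specified AESIs". The SAP builds its AESI tables from the tick on the AE page of the eCRF.

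Elsewhere the condition disappears. The check one hour after dosing in protocol 5.5, and the rows in both visit schedules of Appendix II, refer to inhalation-related reactions or events without it.

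**The concern.** A participant who coughs or has throat irritation from the aerosol, with nothing to suggest allergy, is covered by the mitigation in 4.2.1 but not by the definition that governs the eCRF tick, the AESI report form and the SAP tables. Up to seven sites (protocol 3.6) would have to judge whether a reaction is allergic, and neither document gives a criterion.

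This is the first trial of DZIF-10c by inhalation, and tolerability of inhalation is a primary objective. AESIs are named among the primary target variables (protocol 8.1.3). Participants with AESIs within 7 days are a listed output of both interim analyses (SAP 9.1.1.3 and 9.1.2.3), and the first of these focuses on the dose to take forward. A low AESI count could be read as absence of inhalation reactions when it only reflects absence of allergic ones.

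**Working it through.** The point concerns an event definition. The documents state no AESI rate and no irritation rate, so there is no figure to reproduce. The check sets the texts side by side and follows an irritation event through each capture route.

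**Step 1. Where the allergic condition applies**

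| Place | Function | Allergic presentation required? |
|---|---|---|
| Protocol 4.2.1, airway irritation | Mitigation: AESI solicitation to day 7 | No |
| Protocol 4.2.1, allergic reactions | Mitigation: AESI solicitation to day 7 | No |
| Protocol 5.2.1 | AESI definition | Yes |
| Protocol 5.2.1 | What is solicited to day 7 | Yes |
| Protocol 5.5 | Check 1 h after inhalation or infusion | No |
| Protocol 9.1.1 | AESI definition | Yes |
| Protocol Appendix II A and B | Visit-schedule rows | No |
| SAP 7.8.1 | AESI definition and tables | Yes |

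**Step 2. Which irritation events fall outside**

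- Isolated cough or throat irritation: outside the 5.2.1 definition on a plain reading.
- Bronchospasm from irritation: ambiguous. Bronchospasm is the named example of an allergic presentation, yet 5.2.1 itself says that it can follow either irritation or hypersensitivity. The investigator's tick decides.

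**Step 3. What each route does with a non-allergic irritation event**

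- Serious: reported within 24 hours as an SAE (9.3.1), whatever the mechanism.
- Grade 3 or higher and related, Groups 1A-1C and 2A-2C: reported within 24 hours as a DLT (9.1.6, 9.3.1).
- Grade 3 or higher and related but not serious, Group 2D: no DLT route, because DLTs exist only in dose escalation, and no AESI route. Such events are put to the SMC for review (3.4), but no 24-hour site report is specified.
- Lower grade and not serious, any group: no 24-hour route. As an AE it is collected by open questioning or when volunteered (5.2.1).
- If recorded as an AE within 7 days: counted in the primary endpoint (SAP 7.4.1) and in the tables by organ class and preferred term (SAP 7.8.1).

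**Step 4. Sensitivity of the AESI proportion to one classification**

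- Group 2D arm: 1/20 = 5 percentage points.
- Dose group of three: 1/3 = 33 percentage points.

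These figures show how far one participant moves the result. They do not predict an undercount.

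**The case against.** The strongest reply is that the analysis definition is consistent: protocol 5.2.1, protocol 9.1.1 and SAP 7.8.1 agree, and the risk section is narrative that merely abbreviates. Its paragraph on allergic reactions shortens infusion reactions in the same way. There is also other capture: the 1-hour check, the visit-schedule rows, staff observation during dosing, oxygen saturation, spirometry in Groups 1A-1C, and a diary in Groups 2A-2D that grades cough and shortness of breath through day 28. The SAP's further safety-topic groupings might cover airway events, though their content is not given. How broad an AESI should be is the sponsor's choice, and making every new cough an AESI would pull COVID-19 cough into the rate.

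Much of this stands, and it limits the point. A reader might infer that irritation escapes expedited reporting altogether; it does not, given the SAE and DLT routes. A reader might infer that the primary endpoint loses these events; it does not, if they are recorded. A reader might also infer that all irritant airway narrowing is excluded; for bronchospasm the text is ambiguous.

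The reply does not remove the mismatch. Section 4.2.1 cites AESI solicitation as mitigation specifically for irritation, and 5.2.1 read literally does not deliver it. The other capture is partial. Spirometry is scheduled only for the uninfected groups. The diary serves symptom resolution, not AE reporting. Protocol 9.2.3 treats an event judged to be a sign of the underlying disease as unrelated, so cough after inhalation in an infected participant can be attributed to COVID-19. The placebo arm separates disease cough from drug effect, but inhaled placebo is the formulation buffer and 4.2.1 names excipients as a possible cause. Excipient irritation could therefore appear in every arm and cancel in comparisons, which is why complete absolute counts matter.

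**Conclusion.** The contradiction is real and should be resolved, within a limited scope. Non-serious, non-DLT irritation without an allergic picture is not solicited as an AESI under 5.2.1, has no AESI 24-hour route, and is either absent from the AESI tables or enters them according to each site's reading. In Group 2D this includes non-serious related events of grade 3 or higher.

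The size of any undercount cannot be derived, because the documents give no irritation rate. A statement that an arm would show zero AESIs where the wider reading would show some given percentage needs an assumed irritation rate, and also assumes that every such event is ticked as non-allergic; neither is supported. Nor do the documents show that the primary objective as a whole is under-measured. The conclusion rests on a literal reading of 5.2.1 and on the eCRF tick following that definition. The eCRF itself is not among the documents.

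**What to change.** Use one wording in protocol 4.2.1, 5.2.1, 5.5, 9.1.1 and Appendix II, the eCRF and SAP 7.8.1. Under it, inhalation-related reactions that the investigator judges to be temporally associated with the inhalation are solicited to day 7 whether or not they look allergic. In the SAP, tabulate allergic and non-allergic presentations as separate rows by arm. This keeps the narrow category visible, and the investigator's judgement prevents COVID-19 cough from being counted automatically.

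If the sponsor prefers to keep the narrow AESI, 4.2.1 should stop citing AESI solicitation as mitigation for irritation, and the SAP should tabulate non-allergic inhalation reactions separately.

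The cost is wording in both documents, a few more forms, and a reported rate of inhalation reactions that may look less favourable. Solicitation can be changed only for participants not yet past day 7; the separate tabulation of recorded events can be added at any time before analysis.

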### Dose-Limiting Toxicities

During the dose-escalation phase of the trial (**Groups 1A-1C, Groups 2A-2C**), grade 3 or higher Adverse Events that are deemed to be related to DZIF-10c by the Investigator are considered as Dose-Limiting Toxicities (DLTs). DLTs should be reported to the Sponsor in an expedited manner (see section 9.3.1 for requirements).

### Routine Laboratory Parameters

Routine laboratory parameters from blood and urine samples will be assessed as indicated in the Visit Schedule (see **Appendix II**). Laboratory parameters will include a complete blood count with white blood cell differential, clinical chemistry (Na, K, Cl, Ca, AST, ALT, AP, total bilirubin, creatinine including eGFR, CRP, lipase), coagulation parameters (INR, PTT), urinalysis, and pregnancy testing in women of childbearing potential.

In female participants of childbearing age, the negative result of a serum beta-HCG test or a negative urine dipstick pregnancy test from a sample obtained on the screening day must be available prior to administration of trial medication.

In the event of abnormal laboratory results, participants may be asked to have additional samples collected at the discretion of the investigator or designee.

Abnormal laboratory parameters determined to be clinically significant by the investigator or designee will be graded according to the CTCAE (Common Terminology Criteria for Adverse Events) grading table (v5.0) and reported as Adverse Events.

### Physical Examination and Vital Signs

A general physical examination including weight, height, and examination of skin, respiratory, cardiovascular, nervous, and gastrointestinal systems will be performed at screening. Symptom-directed physical examinations will be performed at later visits as indicated and include vital signs and any further examination indicated by history or observation.

Vital signs to be determined are systolic and diastolic blood pressure, heart rate, respiratory rate, body temperature, and peripheral oxygen saturation.

### Pulmonary function testing

Pulmonary function testing will be performed by spirometry using a hand-held spirometer at screening, prior to the inhalation, and at pre-specified timepoints after the inhalation (see **Appendix II**). FEV1 (forced expiratory pressure in one second), FVC (forced vital capacity), FEV1/FVC ratio, VC (vital capacity), IVC (inspiratory vital capacity), PEF (peak expiratory flow), and PIF (peak inspiratory flow) will be recorded.

### ECG

A 12-lead ECG will be performed at screening and assessed by the Investigators.

### **5.2.2. Pharmacokinetic Assessments**

Non-compartmental analysis methods will be used to calculate pharmacokinetic parameters, and descriptive results will be presented for each dose group. Parameters to be assessed will include

- $AUC_{0-672}$  (the area under the concentration-time curve of DZIF-10c in serum over the time interval from 0 to 672 hours (Day 28)) (secondary endpoint)
- $AUC_{0-504}$  (the area under the concentration-time curve of DZIF-10c in serum over the time interval from 0 to 504 hours) in healthy volunteers
- $AUC_{0-\infty}$  (the area under the concentration-time curve of DZIF-10c in serum over the time interval from 0 extrapolated to infinity)
- $C_{\max}$  (maximum measured concentration of DZIF-10c in serum)
- $t_{\max}$  (time from dosing to  $C_{\max}$  of DZIF-10c in serum)
- $t_{1/2}$  (the terminal elimination half-life of DZIF-10c in serum)

- CL/F (apparent clearance after extravascular administration) for individuals receiving DZIF-10c by inhalation only
- Vz/F (apparent volume of distribution during the terminal phase after extravascular administration) for individuals receiving DZIF-10c by inhalation only

Further PK parameters may be calculated, if considered reasonable.

Data may be used to develop exploratory pharmacokinetic/pharmacodynamic models using non-linear mixed effects techniques, if feasible. Modeling activities will be planned and documented separately. Serum levels of DZIF-10c will be determined using a validated immunoassay [REDACTED].

Exploratory assays for PK analyses under development include serum/plasma neutralization assays against pseudoviruses and authentic SARS-CoV-2. These assays will be performed at the Institutes of Virology at the University Hospital Cologne and/or at the University of Marburg.

### **5.2.3. Assessment of Viral Shedding**

#### SARS-CoV-2 RNA assessment

SARS-CoV-2 RNA levels will be determined from frozen (-80°C) transport medium using a clinically validated quantitative reverse-transcripase real-time PCR assay (qRT-PCR) assay. Results will be provided as Ct (Cycle threshold) values as well as quantitatively (copies/ml) based on a reference standard. These assays will be performed at the Institute of Virology at the University Hospital Cologne.

At the screening visit, a single naso- and/or oropharyngeal swab is sufficient to document the absence or presence of SARS-CoV-2 infection by qRT-PCR. This assay is performed at the trial site's local laboratory. In any case, in SARS-CoV-2-infected individuals, both nasopharyngeal and oropharyngeal swabs must be obtained for the central laboratory prior to study drug administration.

To provide participants with early results about the presence or absence of SARS-CoV-2 in swab samples prior to the determination of results at the central laboratory, an additional oropharyngeal swab may be obtained and sent for NAAT (e.g., qRT-PCR) at the local routine laboratory. This optional additional swab is to be obtained after the oropharyngeal swab for central laboratory evaluation.

### Assessment of the presence of infectious SARS-CoV-2

Viral transport medium will be incubated on VeroE6 cells to determine the presence of infectious virions. Cell culture supernatants will be assessed for virus production by qRT-PCR and/or cells will be visually inspected for the development of cytopathic effects. These assays will be performed at the Institutes of Virology at the University Hospital Cologne and/or the University of Marburg.

### Assessment of viral replication by subgenomic RNA

Levels of subgenomic mRNA that is transcribed in infected cells but not packaged into virions will be determined from RNA extracted from swab samples by qRT-PCR. These assays will be performed at the Institutes of Virology at the University Hospital Cologne and/or the University of Marburg.

#### **5.2.4. Assessment of Anti-Drug Antibodies**

Serum samples will be analyzed for reactivity against DZIF-10c by a validated immunoassay.

#### **5.2.5. Assessment of the Development of Viral Mutations and Antibody Resistance**

Viral RNA will be extracted from transport medium and cDNA will be generated by reverse transcription. Spike sequences will be amplified from cDNA using polymerase chain reaction (PCR) and purified PCR products will be sequenced by Sanger sequencing or next-generation sequencing. Sequences from samples obtained prior to trial drug administration will be compared to sequences obtained after trial drug administration.

Selected recurrent or individual mutations observed in the SARS-CoV-2 S gene will be introduced into plasmids encoding the SARS-CoV-2 S gene by site-directed mutagenesis. Modified plasmids will be used to generate replication-deficient SARS-CoV-2 pseudoviruses and the DZIF-10c sensitivity of unmodified and modified variants will be compared to evaluate the effect of individual spike mutations on antibody sensitivity.

These assays will be performed at the Institutes of Virology at the University Hospital Cologne and/or the University of Marburg.

### **5.2.6. Assessment of COVID-19-related Hospitalizations and Medically-Attended Health Care Contacts**

Any hospitalization and medically-attended health care contact (i.e., health care contacts that were not routine/scheduled visits; including, but not limited to, emergency room visits, unscheduled visits to primary care physicians) reported by participants during the trial duration will be assessed by the investigators based on the available medical information on its relatedness to COVID-19 and conditions associated with SARS-CoV-2-infection.

### **5.2.7. Assessment of Time to Symptom Resolution**

Participants will be asked to self-record selected SARS-CoV-2 symptoms (cough, feverishness, body ache, headache, sore throat, shortness of breath, changes in/loss of taste of taste and smell) from the day of study drug administration through the day 28 visit and grade them as absent, mild, moderate, or severe using a participant diary (**Groups 2A-2D**).

